Appendix 2 Summary of Efficacy Analyses

72 to 120 hours post first dose		End of Therapy Visit (EOT)	Post Treatment Evaluation Visit (PTE)
ITT	ECR	IA	IA
MicroITT	ECR	Micro (by subject)	IA
	ECR (by pathogen)	Micro (by pathogen)	IA (by pathogen)
	ECR (by pathogen and MIC)		IA (by pathogen and MIC)
			Micro (by subject)
			Micro (by pathogen)
emicroITT	ECR		IA (by pathogen)
	ECR (by pathogen)		
CE-EOT		IA	
CE-PTE			IA
ME-EOT		Micro (by subject)	
		Micro (by pathogen)	
ME-PTE			IA
			IA (by pathogen)
			IA (by pathogen and MIC)
			Micro (by subject)
			Micro (by pathogen)

Appendix 3 Adverse Event and Prior/Concomitant Medication Date Imputations

Adverse Event Start/Stop Date Imputation

Imputation Rules for Partial Dates (D = day, M = month, Y = year)

Parameter	Missing	Additional Conditions	Imputation
Start date for AEs	D	M and Y same as M and Y of first dose of study drug	Date of first dose of study drug
		M and/or Y not same as date of first dose of study drug	First day of month
	D and M	Y same as Y of first dose of study drug	Date of first dose of study drug
		Y prior to Y of first dose of study drug but same as Y of screening date	Date of screening date
Stop date for AEs	D, M, Y	None - date completely missing	Date of first dose of study drug
	D	M and Y same as M and Y of last dose of study drug	Date of last dose of study drug
		M and/or Y not same as date of last dose of study drug	Use last day of month
	D and M	Y same as Y of last dose of study drug	Date of last dose of study drug
		Y not same as Y of last dose of study drug	Use Dec 31
	D, M, Y	None - date completely missing	No imputation, but assume ongoing

Note: In all cases, if an estimated start date is after a complete stop date, use the first day of the stop date month.

Similarly, if the estimated stop date is before a complete or imputed start date, use the last day of the start date month.

In all cases, if it cannot be determined if the adverse event occurred prior to or after the first dose of test article, the adverse event should be defined as treatment emergent.

Prior and Concomitant Medication Start Date Imputation

Parameter	Type of Medication	Imputation
Start date for con meds	Non-Antibacterial	If it cannot be determined whether or not the start date of a medication (non-antibacterial) is prior to the first dose of study drug, it will be assumed that the medication was received prior to the first dose of study drug.
	Antibacterial	Missing start dates for antibacterials will be queried for a value. If it cannot be determined whether or not the start date of an antibacterial is prior to the first dose of study drug, it will be assumed that the medication was received prior to the first dose of study drug unless the indication notes that the medication was received after the first dose of study drug.
Stop date for con meds	Non-Antibacterial	If it cannot be determined whether or not the stop date of a medication (^{nonantibacterial}) is after the first dose of study drug, it will be assumed that the medication was received after the first dose of study drug
	Antibacterial	Missing stop dates for antibacterials will be queried for a value. If it cannot be determined whether or not the stop date of an antibacterial is after the first dose of study drug, it will be assumed that the medication was received after the first dose of study drug unless the indication notes that the medication was received prior to the first dose of study drug. If it cannot be determined whether the antibacterial was received prior to the assessment of Early Clinical Response, the EOT and/or the PTE Visit, the antibacterial will be assumed to have been received through the PTE Visit.

Appendix 4 Directionality of Worst Laboratory Parameters

Laboratory Test	Parameter	Worst Value
Hematology	Hematocrit	Lowest value
	Red blood cell count	Lowest value
	Mean cell hemoglobin	Lowest value
	Mean cell hemoglobin concentration	Lowest value
	Hemoglobin	Lowest value
	Mean cell volume	Lowest value
	White blood cell count	Lowest value
	Platelets	Lowest value
	Neutrophils	Lowest value
	Lymphocytes	Lowest value
	Monocytes	Lowest value
	Eosinophils	Highest value
Chemistry	Basophils	Lowest value
	Albumin	Lowest value
	Alkaline phosphatase	Highest value
	Alanine aminotransferase (ALT/SGPT)	Highest value
	Amylase	Highest value
	Aspartate aminotransferase (AST/SGOT)	Highest value
	Urea	Highest value
	Bicarbonate	Lowest value
	Calcium	Both highest value and lowest value
	Cholesterol	Highest value
	Chloride	Both highest value and lowest value
	Creatinine	Highest value
	Creatine kinase (CK)	Highest value
	Gamma-glutamyl transpeptidase (GGT)	Highest value
	Blood glucose	Both highest value and lowest value
	Lactate dehydrogenase (LDH)	Highest value
	Lipase	Highest value
	Magnesium	Both highest value and lowest value
	Phosphate	Both highest value and lowest value
	Potassium	Both highest value and lowest value
	Sodium	Both highest value and lowest value
Coagulation	Total bilirubin	Highest value
	Total protein	Lowest value
	Uric acid	Highest value
	International normalized ratio (INR)	Highest value

Appendix 5 Modified Division of Microbiology and Infectious Diseases Adult Toxicity Table

The DMID Adult Toxicity Table (21-NOV-2007) was modified to exclude the clinical component of the toxicity grading because clinical signs and symptoms related to abnormal laboratory values are not collected in this study. In addition, Grade 0 was added to the table so that shifts from normal could be analyzed. Grades for enzymes were modified as indicated in the table below.

For toxicity grades based on a multiple of the ULN, the normal range from the central laboratory will be applied.

For toxicity grades based on fixed values, the grades will be assigned regardless of the normal actual range values from the central laboratory. For example, a hemoglobin value of 10.0 gm/dL will be assigned a grade of 1 toxicity, even if the lower limit of normal from the laboratory was 9.8 gm/dL.

HEMATOLOGY					
	Grade 0	Grade 1	Grade 2	Grade 3	Grade 4
Hemoglobin (gm/dL)	> 10.5	9.5-10.5	8.0-9.4	6.5-7.9	< 6.5
Absolute Neutrophil Count (count/mm ³)	> 1500	1000-1500	750-999	500-749	< 500
Platelets (count/mm ³)	≥ 100,000	75,000-99,999	50,000-74,999	20,000-49,999	< 20,000
WBCs (count/mm ³)	1000-10,999	11,000-12,999	13,000-14,999	15,000-30,000	> 30,000 or < 1,000

CHEMISTRY

	Grade 0	Grade 1	Grade 2	Grade 3	Grade 4
Hyponatremia (mEq/L)	> 135	130-135	123-129	116-122	< 116
Hypernatremia (mEq/L)	< 146	146-150	151-157	158-165	> 165
Hypokalemia (mEq/L)	> 3.4	3.0-3.4	2.5-2.9	2.0-2.4	< 2.0
Hyperkalemia (mEq/L)	< 5.6	5.6-6.0	6.1-6.5	6.6-7.0	> 7.0
Hypoglycemia (mg/dL)	≥ 65	55-64	40-54	30-39	< 30
Hyperglycemia (mg/dL) (nonfasting and regardless of prior history of diabetes)*	< 116	116-160	161-250	251-500	> 500
Hypocalcemia (mg/dL) (corrected for albumin)	> 8.4	8.4-7.8	7.7-7.0	6.9-6.1	< 6.1
Hypercalcemia (mg/dL) (correct for albumin)	≤ 10.5	10.6-11.5	11.6-12.5	12.6-13.5	> 13.5
Hypomagnesemia (mEq/L)	> 1.4	1.4-1.2	1.1-0.9	0.8-0.6	< 0.6
Hypophosphatemia (mg/dL)	≥ 2.5	2.0-2.4	1.5-1.9	1.0-1.4	< 1.0
Hyperbilirubinemia (total bilirubin)	< 1.1×ULN	1.1-1.5×ULN	> 1.5- 2.5×ULN	> 2.5-5×ULN	> 5×ULN
Urea	< 1.25×ULN	1.25-2.5×ULN	> 2.5-5×ULN	> 5-10×ULN	> 10×ULN
Hyperuricemia (uric acid) (mg/dL)	< 7.5	7.5-10.0	10.1-12.0	12.1-15.0	> 15.0
Creatinine	< 1.1×ULN	1.1-1.5×ULN	> 1.5- 3.0×ULN	> 3.0-6×ULN	> 6×ULN

*The DMID toxicity table reports hyperglycemia detected in nonfasting specimens obtained from subjects with no prior diabetes.

ENZYMES

	Grade 0	Grade 1	Grade 2	Grade 3	Grade 4
AST (SGOT)	< 1.25×ULN	1.25-2.5×ULN	> 2.5-5×ULN	> 5-10×ULN	> 10×ULN
ALT (SGPT)	< 1.25×ULN	1.25-2.5×ULN	> 2.5-5×ULN	> 5-10×ULN	> 10×ULN
GGT	< 1.25×ULN	1.25-2.5×ULN	> 2.5-5×ULN	> 5-10×ULN	> 10×ULN
Alkaline Phosphatase	< 1.25×ULN	1.25-2.5×ULN	> 2.5-5×ULN	> 5-10×ULN	> 10×ULN
Amylase	< 1.1×ULN	1.1-1.5×ULN	> 1.5-2.0×ULN	> 2.0-5.0×ULN	> 5.0×ULN
Lipase	< 1.1×ULN	1.1-1.5×ULN	> 1.5-2.0×ULN	> 2.0-5.0×ULN	> 5.0×ULN

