33 PRESTUDY DOCUMENTATION

The investigator must provide the sponsor with the following documents BEFORE enrolling any subjects:

- Completed and signed form 1572.
- All applicable country-specific regulatory forms.
- Current signed and dated curricula vitae for the investigator, sub-investigators, and other individuals having significant investigator responsibility who are listed on form 1572 or equivalent, or the clinical study information form.
- Copy of the IRB/IEC/REB approval letter for the protocol and informed consent. All advertising, recruitment, and other written information provided to the subject must be approved by the IRB/IEC/REB. Written assurance of continuing approval (at least annually) as well as a copy of the annual progress report submitted to the IRB/IEC/REB must also be provided to the sponsor.
- Copy of the IRB/IEC/REB-approved informed consent document to be used.
- Where applicable, a list of the IRB/IEC/REB members and their qualifications, and a description of the committee's working procedure.
- Copy of the protocol sign-off page signed by the investigator.
- Fully executed CSA.
- Where applicable, a financial disclosure form.
- A written document containing the name, location, certification number, and date of certification of the laboratories to be used for laboratory assays and those of other facilities conducting tests. This document should be returned along with the statement of investigator form. The sponsor must be notified if the laboratory is changed or if any additional laboratory is to be used.
- List of normal laboratory values and units of measure for all laboratory tests required by the protocol. This is required for each laboratory to be used during the study. The sponsor must be notified if normal values or units of measurement change.

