11.4 Laboratory Values

Summaries of laboratory data will include hematology, chemistry, and coagulation (INR only) parameters. Laboratory parameters will be presented in alphabetic order with the following exceptions: differentials of white blood cell (WBC) counts will be presented following the WBC results, and chemistry parameters will first be grouped by organ class (renal, liver, electrolytes, and other) and presented alphabetically within each of these classes, as shown below.

Table 9. Laboratory Parameters and Organ Class

Organ Class	Laboratory Parameter
Renal	Creatinine
Renal	Urea
Liver	Alkaline phosphatase (ALP)
Liver	ALT
Liver	AST
Liver	Total Bilirubin
Liver	GGT
Electrolytes	Bicarbonate
Electrolytes	Calcium
Electrolytes	Chloride
Electrolytes	Magnesium
Electrolytes	Potassium
Electrolytes	Sodium
Other	Albumin
Other	Amylase
Other	Blood glucose
Other	Cholesterol
Other	CK
Other	LDH
Other	Lipase
Other	Phosphate
Other	Total protein
Other	Uric acid

Baseline is defined as the central lab value closest to and prior to the first dose of study drug. If no central lab value is available prior to the first dose of study drug, the local lab value that is closest to and prior to the first dose of study drug will be used as baseline. For by visit analyses, central lab values will be used unless no central lab value was obtained in the visit window. In this case, local lab values will be used for the by visit analyses. All lab values (central and local) are used for determination of the overall worst post-baseline value.

Several analyses of the laboratory data will be presented. Descriptive statistics (based on International System [SI] units) for chemistry, hematology and coagulation values, and the change from baseline will be summarized by treatment group at each time point (Day 4 [+1 day], Day 7 [+1 day], Day 10, EOT Visit and PTE Visit), and for the overall worst value

post-baseline (which includes unscheduled visits). [Appendix 4](#) provides the directionality of the worst values for each laboratory parameter.

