Clinically notable laboratory values will be determined based on the modified Division of Microbiology and Infectious Diseases (DMID) criteria in [Appendix 5](#). Shift tables will be presented to show the number of subjects with a laboratory value with a grade of 0, 1, 2, 3 or 4 at baseline versus the value at each visit and the worst post-baseline value. Number and percentage of subjects with at least a 2-grade increase from baseline (based on DMID criteria) will be summarized by treatment arm. Percentages for each laboratory test will be based on the number of subjects with a baseline and post-baseline evaluation of the specific laboratory test. A listing will be provided which gives all laboratory results for a given laboratory test for subjects who have at least one 2-grade increase from baseline.

The number and percentage (based on the number of subjects with a normal level at baseline) of subjects in each treatment group with an elevated transaminase level ($> 3 \times$ upper limit of normal [ULN], $> 5 \times$ ULN, and $> 10 \times$ ULN), an elevated bilirubin level ($> 1.5 \times$ ULN and $> 2 \times$ ULN) will be presented by study visit. A listing of subjects who meet the laboratory criteria for Hy's law at the same visit will also be provided. The laboratory criteria for Hy's law is defined as 1) ALT or AST $> 3 \times$ ULN, ALP $\leq 2.0 \times$ ULN, and total bilirubin > 1.5 ULN and 2) ALT or AST $> 3 \times$ ULN, ALP $\leq 2.0 \times$ ULN, and total bilirubin $> 2 \times$ ULN.

Detailed subject listings of all laboratory data collected during the study (local and central laboratory data) will be provided, including calculated creatinine clearance (using the Cockcroft-Gault equation). Laboratory values outside normal limits will be identified in the subject data listings with flags for low (L) and high (H) as will laboratory values that meet the clinically notable thresholds (CN).

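### SAP Appendix 5 grades local-laboratory results on the central laboratory's ULN, which can mis-grade those near a cut point for nine analytes

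*Combined protocol and SAP*

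**What the plan says.** SAP 11.4 admits local results in three places.

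- **Baseline:** "If no central lab value is available prior to the first dose of study drug, the local lab value that is closest to" that dose, and prior to it, is used.
- **By visit:** "For by visit analyses, central lab values will be used unless no central lab value was obtained in the visit window". The next sentence reads: "In this case, local lab values will be used for the by visit analyses".
- **Worst value:** "All lab values (central and local) are used for determination of the overall worst post-baseline value".

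SAP 11.4 then says "Clinically notable laboratory values will be determined based on the modified Division of Microbiology and Infectious Diseases (DMID) criteria in" Appendix 5. The shift tables set a "grade of 0, 1, 2, 3 or 4 at baseline versus the value at each visit and the worst post-baseline value", and subjects with a rise of at least 2 grades are counted by arm.

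Appendix 5 fixes the denominator: "For toxicity grades based on a multiple of the ULN, the normal range from the central laboratory will be applied". Grades defined by fixed cut-offs ignore normal ranges altogether. Appendix 4 defines the worst value as the highest value for all nine ULN-multiple analytes.

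Protocol 16.1.3 plans a local sample at Screening only, in parallel with a central one, and sends later samples to the central laboratory. Protocol 16.1.4.4 lets investigators order further local tests. Among the documents that protocol section 33 requires before enrollment is this: "List of normal laboratory values and units of measure for all laboratory tests required by the protocol", for each laboratory used.

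**The concern.** A multiple of the ULN is meant to express a result relative to the range of the laboratory that produced it. If a local result is divided by the central ULN, the quotient mixes two assays or two reference populations, and the grade can change although nothing has happened to the subject.

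The worst-value analysis is the most exposed. At baseline and by visit a local result only fills a gap, but in the worst-value analysis it competes with the central results and replaces them if it is higher. A central baseline set against a local worst value could then show a shift that is partly an artifact of the denominator, or could hide a real one. The tables at stake are hepatic, renal and pancreatic safety tables. The hepatic ones will be read closely, because the protocol background reports ALT increases after iv omadacycline in healthy subjects.

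**Working it through.** **Check on the grade bands.** The one worked example in Appendix 5 is a hemoglobin of 10.0 gm/dL. It falls in the band 9.5-10.5 and is Grade 1, as the SAP says. That is a fixed-value grade; the SAP gives no worked example for a ULN-multiple grade.

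**Inputs from Appendix 5** (lower limits of Grades 1, 2, 3 and 4, as multiples of ULN):

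| Analytes | Cut points |
|---|---|
| ALT, AST, GGT, alkaline phosphatase, urea | 1.25 / 2.5 / 5 / 10 |
| Total bilirubin | 1.1 / 1.5 / 2.5 / 5 |
| Creatinine | 1.1 / 1.5 / 3.0 / 6 |
| Amylase, lipase | 1.1 / 1.5 / 2.0 / 5.0 |

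**Formula.** Let r = local ULN / central ULN. A local result at m times its own ULN is graded under Appendix 5 as m × r. The grade differs from the own-laboratory grade when a cut point k lies between m and m × r, that is, when m lies between k and k/r. The grade is too high if r > 1 and too low if r < 1. Nothing changes if r = 1.

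**Affected intervals for ALT**, in multiples of the local ULN (the values of r are assumptions):

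| r | Intervals | Direction |
|---|---|---|
| 0.8 | 1.25-1.56, 2.5-3.125, 5-6.25, 10-12.5 | too low |
| 1.0 | none | – |
| 1.1 | 1.14-1.25, 2.27-2.5, 4.55-5, 9.09-10 | too high |
| 1.25 | 1.0-1.25, 2.0-2.5, 4.0-5, 8.0-10 | too high |

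**How large a gap matters at Grade 1.** This needs no assumed ULN. A result exactly at the local ULN (m = 1) becomes Grade 1 once r reaches the first cut point. That is a 10% difference for bilirubin, creatinine, amylase and lipase (1 × 1.1 = 1.1), and a 25% difference for ALT, AST, GGT, alkaline phosphatase and urea (1 × 1.25 = 1.25).

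**Illustration with assumed ALT ULNs** (central 40 U/L; none of these ULNs is in the documents):

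| Local result | Local ULN | Appendix 5 rule | Own range |
|---|---|---|---|
| 60 | 60 | 60/40 = 1.50, Grade 1 | 1.00, Grade 0 |
| 110 | 55 | 110/40 = 2.75, Grade 2 | 2.00, Grade 1 |
| 210 | 50 | 210/40 = 5.25, Grade 3 | 4.20, Grade 2 |
| 90 | 32 | 90/40 = 2.25, Grade 1 | 2.81, Grade 2 |

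With a central baseline of 35 (35/40 = 0.875, Grade 0), the local 110 counts as a 2-grade increase under Appendix 5 and as a 1-grade increase on its own range.

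**Check on the obvious repair.** Suppose only the denominator is changed and Appendix 4 is left alone. Take a local ALT of 104 with ULN 65 (104/65 = 1.6, Grade 1) and a central ALT of 101 with ULN 40 (101/40 = 2.525, Grade 2). Appendix 4 picks 104 as the highest value, so the table shows Grade 1 and the Grade 2 result drops out. Selection and grading must therefore change together.

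**The case against.** The best defense is that one common range is a deliberate convention. It sets the same absolute threshold at every site, uses one denominator at baseline and follow-up, and keeps the order of values and the order of grades aligned. Own-laboratory ranges can also create shifts. With assumed ULNs of 40 (central) and 65 (local), an unchanged ALT of 55 goes from 55/40 = 1.375, Grade 1, to 55/65 = 0.85, Grade 0. This stands as a cost of the fix, and the point about ordering stands in full. It does not rescue the present text, which gives no reason for grading a local assay on another laboratory's limit.

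The laboratory analyses are descriptive and the rule is the same in both blinded arms, so no bias between arms is shown. Listings give all local and central values, so single cases can be reviewed. Both points are fair and limit the harm, but absolute counts and individual flags could still be wrong.

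A reader might infer that local results will often supply the worst value, given inpatient iv treatment and about 150 sites. The documents do not support that: later protocol samples go to the central laboratory, and extra local tests are only permitted. Nor do they show that local ranges are already in hand for every affected test. Section 33 covers protocol-required tests, and 16.1.3 names local testing for transaminases, bilirubin and creatinine but not for GGT, alkaline phosphatase, urea, amylase or lipase.

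**Conclusion.** The point holds as a defect in the grading rule. Followed as written, the SAP can mis-grade local results for nine analytes, in either direction, when the local and central ULNs differ and the result lies between k and k/r. This treats the reporting laboratory's range as the proper reference.

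It would go too far to say that local results are mis-graded in general: results away from a cut point and all fixed-value grades are untouched. It would also go too far to say that the Hy's law listing or the transaminase and bilirubin multiple tables are computed on the wrong ULN. The Appendix 5 sentence governs toxicity grades only, and SAP 11.4 names no ULN source for those outputs. That is a gap to fill, not a demonstrated error.

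The size is unknown, since the documents give neither ULNs nor a count of local results; the figures above only illustrate the mechanism. The effect is confined to safety reporting. The efficacy analyses and the sample size are not touched.

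**What to change.** Make three linked changes to the SAP.

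1. **Appendix 5.** Replace the sentence on ULN-based grades with: *Each result graded as a multiple of the ULN is graded on the normal range of the laboratory that reported it. If that range is missing, the central range is used and the result is flagged.*
2. **Worst value.** For the nine analytes, define the worst post-baseline grade as the highest grade (or the highest multiple of ULN) across all graded results, in place of the grade of the highest absolute value under Appendix 4.
3. **SAP 11.4.** State that the same ULN source applies to the transaminase and bilirubin multiple tables, including what counts as normal at baseline, and to the Hy's law listing.

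The cost is a few sentences of SAP text, some reprogramming, and carrying local ranges in the laboratory dataset. Ranges for discretionary local tests may have to be requested. The remaining downside is that a move between laboratories can itself shift a grade, so the shift listings should show which laboratory reported each value.
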